Exposure from the first 12 subjects will be reviewed to confirm that the exposure in the pediatric population is consistent with model predictions from the healthy adult volunteer study. This will occur following at least one dose at the 5 mg/kg dose level and will occur again following at least one dose at 20 mg/kg dose level. Should there be any clinically relevant differences in exposure versus those predicted; a dose adjustment may be made as agreed with the E-DMC. This analysis will be performed by a group of unblinded Clinical Pharmacology scientists not directly involved in the day to day conduct of the study. It is planned that recruitment would continue during this evaluation period.

The study will remain double-blinded until the time of the primary analysis for safety and efficacy (after the last enrolled subject completes 49 weeks). At that time, a limited number of study team members will be unblinded to the treatment assignments. The sites (with the exception of unblinded site personnel eg, the pharmacist) and the subjects will remain blinded to their study treatment through the conclusion of the study.

The following is a schematic of the study design.

Note: Sequence 1, Period 2 demonstrates subjects continuing on the maximum tolerated dose from Period 1 for each individual subject, as per the dose adjustment criteria (Table 2). SCRN=Screening, PBO=Placebo, W=Weeks

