### **3.5.1. Individual Subject Dose Adjustment and Stopping Rules**

The individual dose adjustment will be determined by three parties including the Investigator, sponsor Medical Monitor and a Designated Reviewer.

The dose adjustment criteria described in [Table 2](#) will be used to determine if the dosing or dose level should be:

- Escalated to the next dose level
- Maintained at the current dose level
- Reduced to a lower dose level, or
- Stop dosing.

Following the planned fourth dose within each dose level, all available safety data for an individual subject will be reviewed to determine the appropriate dose adjustment. The Investigator will confirm the number of doses received within the dose level and review all the available safety data along with the sponsor Medical Monitor with the exception of the serum iron indices (serum iron, serum ferritin, TIBC, % transferrin saturation) and the liver MRI results. Findings from the serum iron indices and the liver MRI may inadvertently unblind the Investigator and the sponsor Medical Monitor to the subject's treatment assignment, therefore results from these tests will not be available to the sites or sponsor Medical Monitor for review. Instead, an unblinded Designated Reviewer will review the liver MRI results to monitor for potential iron accumulation. The E-DMC will be unblinded to the serum iron indices and liver MRI results to provide an ongoing safety review of these data.

The Investigator and sponsor Medical Monitor, if necessary will meet to discuss any safety issues and then provide a single recommendation to the unblinded Designated Reviewer who will be separately monitoring the liver MRI results. The Designated Reviewer will collect the safety confirmation from the Investigator and sponsor Medical Monitor and apply the criteria from Table 2 to determine the dose adjustment action. The dose adjustment will then be applied to the subject's assigned treatment, accordingly.

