**Table 2. Criteria to Determine Dose Adjustment within Individual Subjects**

Dose Adjustment Decision	Criteria
Increase Dose Level	E-DMC has not closed the next higher dose level and Subject received $\geq 3$ doses within a the current dose level and Investigator and sponsor Medical Monitor indicate that the current dose level is safe and Designated Reviewer indicates that the liver iron content estimate as determined by R2* value is within the normal range a,d .
Maintain Dose Level	E-DMC indicates that the next higher dose level is closed and/or Subject received $< 3$ doses received within a dose level and Investigator and sponsor Medical Monitor indicate that the current dose level is safe and Designated Reviewer indicates that the liver iron content estimate as determined by R2* is in the normal range a,d .
Reduce Dose Level	E-DMC indicates that the current dose level is closed and the subject is not at the lowest dose level or Subject is not at the lowest dose level and Investigator and sponsor Medical Monitor indicate that the current dose is safe and Designated Reviewer indicates that the liver iron content estimate as determined by R2* value is above the normal range b,d .
Stop Dosing	E-DMC indicates that the current dose level is closed and the subject is at the lowest dose level or Investigator and sponsor Medical Monitor indicate that the current dose is not safe or Designated Reviewer indicates that the liver iron content estimate as determined by R2* value is above the normal range b,d and the subject is at the lowest dose level or Designated Reviewer indicates that the liver iron content estimate as determined by R2* value is within mild overload range c,d .

a. R2\* normal range is  $\leq 75$  Hz at 1.5 T or  $R2^* \leq 139$  Hz at 3.0 T  
 b. R2\* above normal range is  $> 75$  Hz and  $\leq 190$  Hz at 1.5 T or  $R2^*$  is  $> 139$  Hz and  $\leq 369$  Hz at 3.0 T  
 c. R2\* mild overload range is  $R2^* > 190$  Hz at 1.5 T or  $R2^* > 369$  Hz at 3.0 T  
 d. Storey et al, 2007; Wood et al, 2005; Hankins et al, 2009).

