In order to maintain the treatment blind, all subjects regardless of treatment assignment will undergo review for dose adjustment. Subjects who are receiving placebo will have the decision criteria applied, as if they are at the lowest dose level.

The results of the dose adjustment decision (increase, maintain or reduce) *will not* be communicated to the investigator or sponsor medical monitor at any time.

If the Designated Reviewer determines that the subject must stop dosing, he/she will notify the sponsor Medical Monitor who will be responsible for informing the Investigator. In this case, the Designated Reviewer may provide the results of the liver MRI (or iron indices) to the sponsor Medical Monitor. The treatment assignment however, will not be provided.

If dosing is stopped, subjects will continue to be followed for resolution of the safety finding or until a new baseline is established. At any time during the study, either the Investigator and/or sponsor Medical Monitor may determine a safety issue has occurred and it is in the best interest of the subject to stop dosing. In this case, the sponsor Medical Monitor may not overrule the Investigator's decision, nor will the Investigator overrule the sponsor Medical Monitor's decision.

If the E-DMC determines that a dose level should be closed, following their unblinded review of all safety data, no other subjects will be escalated to that dose level. Subjects who are currently dosing within that dose level will be advised by the E-DMC to reduce their dose level.

Subjects in Sequence 2, Period 2, and Sequence 3 Period 1 (who are assigned to placebo), will have dosing terminated should they meet any of the criteria described in [Table 2](#) for "Stop Dosing".

Subjects in Sequence 1 will be treated with their maximum tolerated dose level from Period 1 when they enter Period 2. They will not be escalated to additional higher dose levels in Period 2. For example, if in Period 1, a subject's maximum tolerated dose is 20 mg/kg, they will not be escalated up to 40 mg/kg in Period 2. Although they will not escalate in Period 2, they may have their dose reduced or stop dosing based on the criteria in [Table 2](#).

Subjects, who plan to enroll in the OLE study, will have their *maximum tolerated dose* from study B5161002 be provided by the Designated Reviewer following Week 93 in order to continue on the same dose level in the OLE study without unblinding their treatment assignment in the B5161002 study.

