
### **3.5.2. External Data Monitoring Committee (E-DMC)**

The E-DMC will include experts in the field of neuromuscular diseases and/or statistics. Members of the E-DMC will not be Pfizer employees. The E-DMC will include a Hepatic Expert to review any cases of potential liver toxicity. A patient advocate will also be included on the E-DMC if an appropriately qualified individual can be identified as agreed upon by the E-DMC chairperson. The E-DMC will also include a Cardiology Expert to provide expert interpretation of cardiac MRI or echocardiogram results (as needed). The

E-DMC will be responsible for ongoing unblinded efficacy and safety monitoring (including the liver MRI and iron indices whose results are blinded to the site and study team) per the E-DMC charter from the initiation of the study through the final study visit. Reviews will include aggregate unblinded safety, targeted medical events of special interest including liver toxicity, and serious AE data. The E-DMC may also complete ad hoc safety reviews as described in the E-DMC charter. PK data will be provided to confirm that the exposure in the pediatric population does not exceed the predicted PK stopping limits described below. Ad hoc PK data may be provided to the E-DMC as requested. In addition to the safety reviews, the E-DMC will review the unblinded study data for futility and efficacy at the time of the IA.

Following each data review, the E-DMC will provide a recommendation to the sponsor management to continue the study, modify the study and then continue (eg, terminate a dose level, reduce the liver MRI assessment to annually, remove the manual process for individual dose escalation steps and allow an automated dose-escalation, permit the liver MRI and iron indices data to be provided to the site and blinded study team), or stop the study (eg, due to safety). The recommendations made by the E-DMC to alter the conduct of the study will be forwarded to the sponsor management for final decision. The sponsor management will forward such decisions, which may include summaries of aggregate analyses of endpoint events and of safety data that are not endpoints, to regulatory authorities, as appropriate. At any time the E-DMC may indicate that the limit of safety and/or tolerability has been reached and that any of the dose levels will be removed from the study.

The E-DMC will consider the following safety criteria during their safety review:

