## **5.4. Breaking the Blind**

This study is intended to be conducted as double-blind. The subject, investigator and sponsor will be blinded to the randomized study treatments. The Designate Reviewer (described in [Section 3.5](#)) and the pharmacists will be identified as unblinded as they will need to communicate regarding subject dose level adjustments. The unblinded pharmacist will receive and prepare study drug. Other unblinded individuals (eg, site monitors, clinical pharmacology, E-DMC) will be prospectively identified with their study roles.

A PK/PD unblinding plan approved by the clinical lead, clinical pharmacology lead and statistical lead will be in place to describe the procedures to be employed in safeguarding the study blind for members of the PF-06252616 study team. Under this plan a group of Statisticians, PK/PD data provider, PK/PD analyst and PK/PD support would be unblinded in order to aid in analyzing the PK and PD data as well as to initiate the building of statistical models of the PK, as well as exposure/response analysis models and conduct associated simulations.

The aim of this work will be to facilitate review of PK/PD data for a fuller interpretation of the study upon completion (or at appropriate milestones). This group will not serve on the study team while the study is fully blinded prior to the primary analysis being performed. The details of the procedures will be described in the PK/PD unblinding Plan for Modeling and Simulation for Study B5161002.

At the initiation of the study, the study site will be instructed on the method for breaking the blind. The method will be an electronic process. Blinding codes should only be broken in emergency situations for reasons of subject safety. Whenever possible, the investigator or sub-investigator consults with a member of the study team prior to breaking the blind. When the blinding code is broken, the reason must be fully documented and entered on the CRF.

The study site pharmacists should not release unblinding information to the other study staff, instead the formal IRT procedure should be used. Aside from such emergent subject safety situations, information of study treatment including sequence group, subject dose level and randomized study treatment will be kept confidential and will not be released to the investigator/study staff until the conclusion of the study.

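### When the E-DMC closes a dose level, Protocol 3.5.1 has boys at that level advised to reduce; above the lowest level this identifies them as on active drug, and it does not fit Table 2 or Section 3.5.2

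*Protocol*

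**What the plan says.** The sentence at issue stands in Protocol Section 3.5.1, in the text after Table 2. If the E-DMC decides that a level should be closed, nobody else is escalated to it, and "Subjects who are currently dosing within that dose level will be advised by the E-DMC to reduce their dose level". It gives no route, no date and no exception for the lowest level.

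The surrounding rules are:

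- **Confidentiality of the decision (3.5.1, after Table 2).** The outcome of an increase, maintain or reduce decision will not "be communicated to the investigator or sponsor medical monitor at any time".
- **Placebo boys (3.5.1, after Table 2).** "Subjects who are receiving placebo will have the decision criteria applied, as if they are at the lowest dose level".
- **Blinding of subjects (3.1).** Apart from unblinded site staff, sites stay blinded, and "the subjects will remain blinded to their study treatment through the conclusion of the study".
- **Confidentiality of dose (5.4).** Outside emergency unblinding, "information of study treatment including sequence group, subject dose level and randomized study treatment will be kept confidential". The same section has the Designated Reviewer and the pharmacists unblinded so that they can deal with each other on dose changes.
- **Table 2.** The criterion "E-DMC indicates that the current dose level is closed" appears in two rows. It leads to Reduce if the boy is above the lowest level and to Stop Dosing if he is at it.
- **Timing (3.5.1).** "Following the planned fourth dose within each dose level, all available safety data for an individual subject will be reviewed". Section 3.1 puts these reviews at Weeks 13, 29 and 45 in Period 1 and Weeks 61 and 77 in Period 2.
- **Authority (3.5.2).** "The recommendations made by the E-DMC to alter the conduct of the study will be forwarded to the sponsor management for final decision". Terminating a dose level is one of the examples given there of a change that the E-DMC may recommend.

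**The concern.** Read as written, the sentence has boys told something that can be true only of active treatment. The primary endpoint is a timed stair climb, a performance test run by site evaluators (Sections 7.8 and 7.8.2), and knowledge of assignment can affect how it is performed and timed. The plan guards against weaker clues than this one: it withholds liver MRI and iron results (3.5.1) and masks the infusion bag, drip chamber and in-line filter (5.7). A closure during Period 1 could therefore compromise the primary comparison for the boys concerned, and also for boys at the same stage who receive no such advice.

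The second issue is operational. A closure is the level-wide safety action in this trial, and the text leaves unsettled when it takes effect, what happens at the lowest level, who decides, and which Table 2 row governs if two apply.

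**Working it through.** The plan states no figure on this point, so there is none to reproduce. The check sets the passages side by side and adds two short calculations.

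**1. Who can be told to reduce.** Table 2 allows the Reduce decision only for a boy above the lowest level. Section 3.5.1 treats every placebo boy as being at the lowest level. Hence P(advised to reduce | placebo) = 0.

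**2. What the advice reveals.** Section 9.1 gives 70 boys on active drug and 35 on placebo in Period 1.

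- Before any advice: P(active) = 70/(70 + 35) = 0.667.
- After advice, with s the share of active boys at that stage who are at the closed level: P(active | advised) = 70s/(70s + 35 × 0) = 1, for any s above 0.
- For boys at the same stage who are not advised: P(placebo | not advised) = 35/(35 + 70(1 − s)). The documents do not give s, so it is an assumption:
  - s = 0.25: 35/87.5 = 0.40
  - s = 0.50: 35/70 = 0.50
  - s = 0.80: 35/49 = 0.71
  - s = 1: 35/35 = 1.00

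  The starting value is 35/105 = 0.333.

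**3. The lowest level.** If 5 mg/kg were closed and Table 2 followed, active boys at that level and placebo boys would both meet Stop Dosing, so the action would not separate the arms. The unblinding therefore concerns the levels above it, planned in Period 1 for Weeks 17 to 29 (20 mg/kg) and Weeks 33 to 45 (40 mg/kg) in Table 3. At the lowest level the problem is a different one: the sentence says reduce and Table 2 says stop.

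**4. Effective date.** Section 3.5.2 lets the E-DMC act whenever it judges a limit to be reached. The closure sentence has no date. Individual review follows the planned fourth dose, and Section 5 (text after Table 4) places reductions for poor tolerance at the point of escalation. With infusions at Weeks 1, 5, ..., 93 and reviews at Weeks 13, 29, 45, 61 and 77, the further infusions at a closed level are:

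- Closure takes effect at once: 0.
- Closure waits for review and follows the first dose of a block: 3. For example, after Week 17 there remain Weeks 21, 25 and 29.
- Closure waits for review, falls just after a review, and the boy stays at that level: 4. For example, after Week 61 there remain Weeks 65, 69, 73 and 77.
- Closure just after the Week 77 review: Weeks 81, 85, 89 and 93 remain, with no later review listed.

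**5. Authority.** Section 3.5 says the E-DMC may determine that a level be closed, and the closure sentence has the E-DMC advising subjects. Section 3.5.1 gives individual adjustment to three parties: the Investigator, the Medical Monitor and the Designated Reviewer. Section 3.5.2 makes closing a level a recommendation on which sponsor management decides.

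**6. Overlapping rows.** In Table 2 the closure limb of Reduce carries no condition on safety or on R2*. A boy above the lowest level at a closed level who is also judged not safe, or whose R2* is in the mild overload range, meets both Reduce and Stop Dosing. No order of precedence is given.

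**The case against.** The strongest reply is that the sentence is loose drafting. Nothing else in the protocol gives the E-DMC a channel to families. Its output goes to sponsor management (3.5.2), the Designated Reviewer applies Table 2 (3.5.1) and deals with the pharmacists (5.4), and unblinded site staff may pass no assignment information to subjects (5.6.2). On that view the sentence means only that the E-DMC advises that these boys be reduced. This is plausible, and it rules out one inference that a reader might draw, that the plan sets out to unblind. But the sentence names the subjects as the recipients and does not refer to the blinded route, and it would be acted on under pressure. The ambiguity stands.

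Some further inferences are tempting and are not supported:

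- **That a closure would unblind up to 70 boys.** Seventy is everyone allocated to active drug, accumulated over 30 months of enrolment (3.3). It is not the number at a level when it closes, and it would include the lowest level, where Table 2 does not separate the arms.
- **That boys not advised are necessarily likely to be on placebo.** This depends on the assumed share s; at 50% it is an even chance.
- **That the text fixes two conflicting dates.** Section 3.5.1 does not say that Table 2 can be applied solely after the fourth dose, and the Section 5 text on reductions concerns tolerance, not closure. The gap is a missing effective date.
- **That any boy just past a review faces 4 more infusions at the closed level.** Most boys who pass the Week 13 or Week 29 review move up, and Sequence 2 goes to placebo after Week 45. The figure applies mainly to Sequence 1 in Period 2 and to boys maintained at a level.

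It is also fair to say that the lowest-level conflict can be resolved by treating Table 2 as the more specific rule, that the overlap in Table 2 is a minor matter of precedence, and that the E-DMC charter, which is not among the documents, may settle the question of authority. None of this makes the closure sentence consistent with the text around it.

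**Conclusion.** The point holds as a defect of wording with a real consequence if the wording is followed. Above the lowest level, a boy advised to reduce is identified as on active drug (2/3 to 1 in Period 1), contrary to the non-communication rule in 3.5.1 and to Sections 3.1 and 5.4. The sentence also conflicts with Table 2 at the lowest level and with Section 3.5.2 on who decides. The effective date of a closure is unstated, which leaves between 0 and 3 further infusions at a closed level after the first dose of a block, or up to 4 for a boy who stays at that level after a review.

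The conclusion rests on the literal reading of the sentence, on the 70:35 allocation, and on a closure occurring; without a closure there is no effect. The primary comparison is exposed only if the closure comes before the boys concerned have had their Week 49 assessment.

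**What to change.** Replace the closure sentence in Section 3.5.1. The new text should say that, once a closure is decided, any resulting change for an individual boy is carried out by the unblinded Designated Reviewer through the unblinded pharmacist, and that no reduction is disclosed to the boy, caregiver, investigator or Medical Monitor. Sponsor management would still be informed as Section 3.5.2 requires.

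Then reconcile that text with Table 2, Sections 3.5 and 3.5.2, the review timing in 3.5.1 and the Section 5 text after Table 4, so that the protocol states:

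- what applies when the closed level is the lowest;
- when a closure takes effect relative to the next infusion and the next scheduled review, including after Week 77;
- whether the E-DMC or sponsor management decides;
- which Table 2 row governs when a boy meets both Reduce and Stop Dosing.

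The clinical choices among these belong to the sponsor and the E-DMC. The cost is a few sentences in Section 3.5.1, Table 2 and the E-DMC charter. The unblinded roles already exist, so no new staff or procedure is needed.

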
### **3.5.2. External Data Monitoring Committee (E-DMC)**

The E-DMC will include experts in the field of neuromuscular diseases and/or statistics. Members of the E-DMC will not be Pfizer employees. The E-DMC will include a Hepatic Expert to review any cases of potential liver toxicity. A patient advocate will also be included on the E-DMC if an appropriately qualified individual can be identified as agreed upon by the E-DMC chairperson. The E-DMC will also include a Cardiology Expert to provide expert interpretation of cardiac MRI or echocardiogram results (as needed). The

E-DMC will be responsible for ongoing unblinded efficacy and safety monitoring (including the liver MRI and iron indices whose results are blinded to the site and study team) per the E-DMC charter from the initiation of the study through the final study visit. Reviews will include aggregate unblinded safety, targeted medical events of special interest including liver toxicity, and serious AE data. The E-DMC may also complete ad hoc safety reviews as described in the E-DMC charter. PK data will be provided to confirm that the exposure in the pediatric population does not exceed the predicted PK stopping limits described below. Ad hoc PK data may be provided to the E-DMC as requested. In addition to the safety reviews, the E-DMC will review the unblinded study data for futility and efficacy at the time of the IA.

Following each data review, the E-DMC will provide a recommendation to the sponsor management to continue the study, modify the study and then continue (eg, terminate a dose level, reduce the liver MRI assessment to annually, remove the manual process for individual dose escalation steps and allow an automated dose-escalation, permit the liver MRI and iron indices data to be provided to the site and blinded study team), or stop the study (eg, due to safety). The recommendations made by the E-DMC to alter the conduct of the study will be forwarded to the sponsor management for final decision. The sponsor management will forward such decisions, which may include summaries of aggregate analyses of endpoint events and of safety data that are not endpoints, to regulatory authorities, as appropriate. At any time the E-DMC may indicate that the limit of safety and/or tolerability has been reached and that any of the dose levels will be removed from the study.

The E-DMC will consider the following safety criteria during their safety review:

- The number of subjects who have severe AEs or serious AEs in the same organ system which are determined to be related to study medication (active treatment, not placebo).
- The exposure within a dose level which approximately reaches or exceeds the PK stopping limits of predicted  $C_{av}$  of 2690 mg/mL and  $C_{max}$  of 1870 mg/mL (exposures obtained at the monkey NOAEL dose of 50 mg/kg). Modified doses may be considered if they are not expected to exceed PK stopping criteria.
- Other findings that may indicate that a dose level should be closed.

Details of the type, timing and responsibilities of the E-DMC will be included in the E-DMC charter.

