### **1.9. Rationale for Dosage Selection and Method of Administration**

For Study B5161002, 5 mg/kg administered over two hours and every 4 weeks is being proposed as the starting dose as it is expected to show median GDF-8 serum coverage over 80%, and therefore may show pharmacology as well as further provide a safety multiple of 17 and 28.6 for  $C_{max}$  and  $C_{av}$  at steady state respectively. 20 mg/kg administered over two hours and every 4 weeks is being proposed as the dose that would provide target coverage similar to the 10 mg/kg Q 2 week dose in Study B5161001, which produced MRI signal changes in healthy volunteers. 40 mg/kg administered over two hours and every 4 weeks is being proposed as the highest dose as it will provide additional safety coverage for future studies and it maximizes the potential for efficacy, especially considering that the target engagement of PF-06252616 in muscles is unclear. IV was chosen as the route of administration to support the large volume of the dose that will be required to obtain the targeted GDF-8 coverage as well as for subject adherence. The frequency of administration was chosen as 4 weeks to achieve targeted GDF-8 coverage but also to reduce the burden on subject travel to study sites.

To arrive at the above doses and regimens PK and PK/PD approaches were considered using the data previously generated within the program. As prior PF-06252616 PK data has been derived in an adult population, a literature review was conducted to determine the CL and  $V_{ss}$  parameters of monoclonal antibodies administered to both an adult and a pediatric population. This meta-analysis suggested that both parameters were similar between the adults and children, especially when both populations received a body weight based (mg/kg) dosing. To confirm allometry for the current monoclonal antibody, allometric scaling of non-compartmental PK parameters (CL and  $V_{ss}$ ) determined in mice, rat, monkey and adult humans (Study B5161001) were scaled with body weight. The exponents obtained were 0.79 and 0.94 for CL and  $V_{ss}$  respectively suggesting that PF-06252616 is similar to other monoclonal antibodies and that the PK parameters scale allometrically.

Predicted CL and  $V_{ss}$  parameters were generated across the population using both the allometrically scaled non-compartmental parameters and allometrically scaled (using a fixed

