From a PK/PD consideration, a target mediated drug disposition model (TMDD) was developed to simulate PF-06252616 exposures and corresponding GDF-8 coverage. For Study B5161002 PK and GDF-8 simulations, it was assumed that the weight normalized population PK parameters and the GDF-8 binding parameters are similar between healthy adult volunteers and DMD subjects 6 to 10 years old. These parameters were used to simulate both the expected PK profile (to compare to toxicology exposure margins) and the expected PD profile (considering target coverage in serum). These simulations suggest that 5 mg/kg PF-06252616 when administered over a 2-hour infusion duration and every 4 weeks provides a median (50th percentile) GDF-8 coverage of approximately 85% with a lower end prediction (5th percentile of the trough) of 61% coverage at steady state. This dose was determined to be a suitable starting dose in Study B5161002 as an impact on the pharmacology may be expected and there are wide safety margins to the toxicology limits (Table 1). Similarly, simulations suggest that 20 mg/kg PF-06252616 when administered over a 2-hour infusion duration and every 4 weeks may provide a median target coverage of approximately 95% with the lower end of the prediction (5th percentile of the trough) of 87% at steady state. These values are very similar to the estimated GDF-8 coverage for the 10 mg/kg dose administered every 2 weeks in Study B5161001 which produced a MRI signal on Day 113. Finally, simulations suggest that a 40 mg/kg dose administered every 4 weeks will provide median target coverage of approximately 97% with a lower end (5th percentile of the trough) of around 93% at steady state. At the highest dose, it is anticipated that a 2-fold safety margin to the toxicology limits will be maintained (Table 1).

**Table 1. Escalating Dose Cohorts and Predicted Exposures and Margins Relative to Toxicokinetics Limits at Planned PF 06252616 Doses**

IV Dose (mg/kg)	Predicted C max (µg/mL)	Safety margin to toxicology limit (C max )	Predicted C av	Safety margin to toxicology limit (C av )
5	158	17	65	28.6
20	598	4.5	265	7.1
40	1214	2.2	550	3.4

a Toxicology limit set by the NOAEL of 26 week non-human primate juvenile study at 50 mg/kg [Cmax = 2690 µg/mL, Cav,ss = 1870 µg/mL].  

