 The toxicology AUC168 314,000 µg·hr/mL was converted to Cav as follows: 314000 ÷ 168 = Cav. The predicted human AUC672 369298 µg·hr/mL was converted to Cav as follows: 369298 ÷ 672 = 550 µg/mL  
 Cmax = maximum concentration at steady state; Cav = average concentration at steady state.

090177e1909dc770\Approved\Approved On: 25-Mar-2019 05:50 (GMT)

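### The E-DMC's PK stopping limits in Protocol 3.5.2 have the Cav and Cmax labels exchanged and are printed in mg/mL, contradicting the Table 1 footnote for the same monkey NOAEL.

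*Protocol*

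**What the plan says.** Section 3.5.2 of the Protocol lists the safety criteria the E-DMC is to consider. One is exposure within a dose level that comes close to or passes "PK stopping limits of predicted $C_{av}$ of 2690 mg/mL and $C_{max}$ of 1870 mg/mL (exposures obtained at the monkey NOAEL dose of 50 mg/kg"). The same item lets modified doses be considered only if they are not expected to breach these criteria. Earlier in the section the purpose is explicit: "PK data will be provided to confirm that the exposure in the pediatric population does not exceed the predicted PK stopping limits described below".

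Section 1.9 describes the same NOAEL. The Table 1 footnote sets the toxicology limit from the 26-week juvenile monkey study at 50 mg/kg as "C max = 2690 µg/mL, C av,ss = 1870 µg/mL", and shows where the Cav comes from: "314,000 µg·hr/mL was converted to C av as follows: 314000 ÷ 168 = C av". The text of section 1.9 says the 5 mg/kg starting dose will "provide a safety multiple of 17 and 28.6 for $C_{max}$ and $C_{av}$ at steady state respectively", and that at the highest dose "it is anticipated that a 2-fold safety margin to the toxicology limits will be maintained".

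**The concern.** The two sections use the same pair of numbers for the same animal dose, but section 3.5.2 attaches them to the opposite parameters and in a unit 1,000 times larger. Both cannot be right, and a Cav above the Cmax is impossible for a single concentration profile.

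The figures in section 3.5.2 are the ones with a decision attached. PK data go to the E-DMC to be compared with them, and they also bound any modified dose. Section 3.1 allows alternative dose levels, and the section 1.9 simulations assumed boys aged 6 to 10 while section 4.1 admits boys up to <16. The check of observed exposure against a limit is therefore not a formality.

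**Working it through.** **Inputs, all from Protocol section 1.9 (Table 1 and its footnote) and section 3.5.2**
- Monkey NOAEL, footnote: Cmax 2690 µg/mL, Cav 1870 µg/mL, AUC168 314,000 µg·hr/mL.
- Monkey NOAEL, section 3.5.2: Cav 2690 mg/mL, Cmax 1870 mg/mL.
- Predicted human Cmax at 5, 20 and 40 mg/kg: 158, 598, 1214 µg/mL.
- Predicted human Cav at the same doses: 65, 265, 550 (the footnote gives µg/mL for the 550).
- Predicted human AUC672 at 40 mg/kg: 369,298 µg·hr/mL.

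**1. Which number is the Cav?** Cav = AUC ÷ interval.
- Monkey: 314,000 ÷ 168 = 1,869 µg/mL, which is the 1870.
- Human, 40 mg/kg: 369,298 ÷ 672 = 549.6 µg/mL, which is the 550 in the table.

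**2. Which labels reproduce Table 1?** Margin = toxicology limit ÷ predicted exposure, in µg/mL.

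| Dose (mg/kg) | Parameter | Table 1 margin | Footnote labels | Section 3.5.2 labels |
|---|---|---|---|---|
| 5 | Cmax | 17 | 2690/158 = 17.0 | 1870/158 = 11.8 |
| 20 | Cmax | 4.5 | 2690/598 = 4.5 | 1870/598 = 3.1 |
| 40 | Cmax | 2.2 | 2690/1214 = 2.22 | 1870/1214 = 1.54 |
| 5 | Cav | 28.6 | 1870/65 = 28.8 | 2690/65 = 41.4 |
| 20 | Cav | 7.1 | 1870/265 = 7.1 | 2690/265 = 10.2 |
| 40 | Cav | 3.4 | 1870/550 = 3.40 | 2690/550 = 4.89 |

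The footnote labels reproduce every margin. The 28.6 against 28.8 is rounding: a Cav of 65 can stand for 64.5 to 65.5, and 1,869/65.5 to 1,869/64.5 is 28.5 to 29.0. The labels of section 3.5.2 reproduce none. They would also leave only a 1.54-fold Cmax margin at 40 mg/kg, against the 2-fold margin claimed in section 1.9.

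**3. Size of the error as printed (mg/mL).**
- Cmax: 1,870,000 ÷ 1214 ≈ 1,540 times the predicted 40 mg/kg value.
- Cav: 2,690,000 ÷ 550 ≈ 4,891 times the predicted value.

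**4. Size if the unit is read as µg/mL and only the labels are wrong.**
- Cmax limit: 1870/2690 = 0.70, so 30% too low.
- Cav limit: 2690/1870 = 1.44, so 44% too high.

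**5. Effect on the rule.** Section 3.5.2 does not say whether one limit suffices or both are needed. Scaling the predicted 40 mg/kg profile proportionally, the intended limits are reached at 2.22 times (Cmax) and 3.40 times (Cav) prediction, and the exchanged limits at 1.54 and 4.89 times.
- Either limit suffices: the rule acts at 1.54 instead of 2.22 times prediction, so it is stricter. It can never be looser on this reading. Any profile meeting an intended limit has Cmax of at least 1870, because Cav cannot exceed Cmax. The rules differ only for Cmax between 1870 and 2690 with Cav below 1870.
- Both limits needed: the rule acts at 4.89 instead of 3.40 times prediction, so it is looser. The rules differ only for Cav between 1870 and 2690 with Cmax at or above 2690.

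**The case against.** The label exchange is not in dispute; the case on the other side concerns the unit and the consequences.

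- **The unit may be a reading artefact.** A µ can be read from a PDF as an m. Section 1.7 contains another implausible unit, a baseline myostatin in mg/mL followed by ng/mL values for the same analyte, so unit prefixes in the available text are not uniformly reliable. Against this, µg/mL reads correctly in the Table 1 footnote, and mg/mL is what section 3.5.2 shows. The caveat stands for the unit and has no bearing on the labels.
- **An expert committee would notice.** Section 3.5.2 names the source of the limits, Table 1 has the right figures, and a Cav above a Cmax is visibly impossible. That makes literal use unlikely, but a reader who noticed only the unit would still apply the wrong limit to each parameter.
- **The limits are not an automatic trigger.** They are one item for consideration, and the E-DMC may close a dose level at any time on other grounds. Its detailed procedures are in a charter that is not among the documents and may carry correct figures. This limits the likely harm.
- **Other PK safeguards exist.** Section 3.1 compares exposure in the first 12 subjects with model predictions: "This will occur following at least one dose at the 5 mg/kg dose level", and again after 20 mg/kg, with dose adjustment possible. The first 12 subjects also have extra PK visits during the 40 mg/kg interval, and the E-DMC can ask for further PK data. These are real protections, but the formal comparison with predictions does not name 40 mg/kg, where the margin is smallest.
- **The exchange may be conservative.** With the unit corrected and either limit sufficient, it is. With both required, it is not, and the text does not settle which applies.

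**Conclusion.** The concern holds. Section 3.5.2 states a safety threshold for a pediatric trial that is wrong as written, and section 1.9 of the same protocol shows the correct values: Cmax 2690 µg/mL and Cav 1870 µg/mL. The exchange of labels is certain; the mg/mL unit is as printed, subject to the reading caveat. This is a transcription error, since the Table 1 arithmetic itself reproduces.

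Taken literally, the limits could not be reached. Taken in µg/mL, one is 30% too low and the other 44% too high. The net effect is then stricter or looser depending on an unstated either/both rule; the multiples given for that assume exposure scales in proportion to the predicted 40 mg/kg profile. No misapplication is shown, and no efficacy analysis, sample size or type I error is affected. The point still requires correction because the trial relies on these figures for dose-level decisions and for bounding modified doses.

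**What to change.** In section 3.5.2, change the limits to Cmax of 2690 µg/mL and Cav of 1870 µg/mL, after checking both against the source toxicokinetic report. Confirm that the E-DMC charter carries the same figures, and notify the E-DMC of the correction. While the line is open, it would help to state whether reaching either limit is enough.

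The cost is a one-line protocol correction or administrative letter, a check of the charter and a note to the committee. Trial conduct does not change. This correction restores the limits section 1.9 already describes; it takes no position on what the clinical limit ought to be.
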